### **Potential Benefits and Risks to Patients**

Every effort is taken to ensure that screening and production of the clinical trial follows a code of ethics. Patients are not at risk of contracting harmful diseases, ailments, or any other negative symptoms. The trial is held in a COVID-19 safe environment, with regular cleaning, monitoring, and health checks performed regularly by staff.

Patient and staff safety is a priority of the clinical trial. To ensure this, potential patients were screened and interviewed in advance of the trial to ensure that they fit the correct profile for the study. They were asked about their medical history, and the accessibility of the clinical trial location in relation to their home. The clinical trial timeframe was agreed upon with all patients to ensure they arrived at their session at the correct time. Patients had the option to drop out of the clinical trial at any point.

There have been no recorded negative side effects to Pulsed Electromagnetic Therapy in the treatment of patients. In the clinical experience of the Investigator, approximately 1% of patients have reported experiencing headaches or dizziness during and/or immediately after a session using the SCIO device. This side effect was not reported to be severe and did not last longer than 12 hours.

Therefore, it is prudent to assume that there will not be any negative health side effects from this clinical trial. Patients were made aware of this potential side effect prior to the trial.

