### **During The Trial**

There were no changes to the initial plan for the clinical trial. All patients attended their arranged appointments and reported no negative side effects to the treatment.

The Lead Practitioner noted valuable verbal feedback during sessions with each patient.

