## Discussion

Regarding nearly all the symptoms analysed in the clinical trial, there was a mild to significant improvement. The largest improvement of an average of 2.6 points was discovered in symptoms related to insomnia and anger outbursts. It can be hypothesised that due to increased rest and relaxation, patients were able to manage their negative emotions more efficiently.

Positive results were also found within the patients' own value of life. Large improvements were found in a patients' perception of overall happiness, satisfaction and fulfilment, as well as general quality of life. All these values increased by a score of 2 or more on average. It is evident that the PEMF treatment is beneficial in providing patients with a relaxing and calm therapy which in turn helps appreciation for quality of life, and motivation in facing daily tasks head on.

Physical symptoms were also improved using PEMF therapy. Issues relating to headaches, fatigue, and flashbacks were all reduced over the course of the trial. Patients reported feeling more relaxed, and physical pains has subsided (See 'Patient Four' below).

It is important to note that the only symptom that experienced no average change was depression. It can be postulated that this is due to depression being a more deep-rooted issue which was prevalent for an extended period prior to the clinical trial. It is promising to see that cases of depression were not worsened during the trial, indicating that PEMF therapy is able to improve symptoms related to depression (fatigue, insomnia, anger). Nonetheless, the lack of change in depression forms a consideration for future clinical trials (see 'Considerations').

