## **Reflections and Considerations**

The clinical trial highlights the many benefits of PEMF therapy in treating symptoms related to PTSD and Trauma. All patients felt a significant improvement in their lives and indicated a wish to continue with PEMF therapy after the clinical trial had concluded. It can also be suggested that taking the time out of a daily schedule to attend PEMF therapy allows a patient to relax and rest. This form of meditation can be hypothesised as a beneficial side effect to PEMF therapy.

It should also be noted that patients with previous experience with Cognitive Behavioural Therapy (CBT) were more receptive to treatment, especially within the first two sessions. This is due to the selected patients (two of the five patients in the study) being able to communicate their triggers and emotions more clearly to the Lead Practitioner during PEMF treatment. This allowed the patients to experience a form of CBT with the clinical trial staff, whilst providing them time to relax out of their regular schedule. These two patients especially saw an improvement with sleeping, indicating that the opportunity to vocalise their symptoms and emotions helped them alleviate PTSD-related problems.

Whilst the clinical trial was a success in achieving the primary objective, there are numerous considerations and reflections for further clinical trials into PEMF therapy.

- A larger study would be beneficial in further analysing the benefits of PEMF therapy in treating PTSD and Trauma. Access to a larger cohort of volunteers, with a larger time frame of more PEMF sessions would produce a larger result pool. This would also allow for a control group, a treatment group, and a sham group to compare results more accurately and draw wider conclusions to the specific benefits of PEMF treatment.
- Twice weekly sessions proved to be tiring for patients (see Patient Three's statement above), therefore a longer, more spaced-out study would allow patients to recover from PEMF treatment before their subsequent sessions. This would remove the risk of exhausting the patients which may hamper accurate results of the study.
- This study was restricted due to financial and time restraints. Staff numbers were restricted to the Lead Practitioner and a Research Assistant to disseminate results. The financial impact of conducting a clinical trial for free dictated that the trial would be short to make it viable for the sponsor's funding.

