It is of the opinion of the National Centre of Electromagnetic Therapies that this clinical trial was a success in meeting its primary objective in improvement symptoms related to PTSD and Trauma through PEMF. The clinical trial has highlighted the many benefits of PEMF treatment. Nearly all studied symptoms improved for all patients during the trial, and there was no worsening of symptoms recorded. The evidence provided within this document attests to these conclusions.

Therefore, it is recommended that further clinical trials into the development of Pulsed Electromagnetic Therapy as treatment for symptoms of PTSD and Trauma should be conducted. It is our goal to conduct a similar study on a far larger scale, with more participants and a longer trial period. This conclusion has been reached due to the promising positive benefits of PEMF therapy shown through this clinical trial. The clinical trial also concludes that PEMF therapy is a beneficial, non-invasive alternative to prescription medication in relation to PTSD and Trauma. Whilst the results cannot claim to be representative of the entire U.K., the clinical trial has indicated that there are significant benefits to Bio-Resonance treatment and should therefore be studied further.

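### The no-side-effects statement conflicts with tiredness reported later, and the group means alone do not show that no patient worsened

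*Combined protocol and SAP*

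**What the plan says.** All of the text is in the combined protocol and SAP.

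**Side effects.** During The Trial states: "All patients attended their arranged appointments and reported no negative side effects to the treatment". Reflections and Considerations then lists, among lessons for the next study: "Twice weekly sessions proved to be tiring for patients". It refers the reader to Patient Three's statement, says that "a longer, more spaced-out study would allow patients to recover from PEMF treatment before their subsequent sessions", and adds: "This would remove the risk of exhausting the patients which may hamper accurate results of the study". Potential Benefits and Risks to Patients describes headache or dizziness in about 1% of the investigator's patients and says of it: "This side effect was not reported to be severe and did not last longer than 12 hours". Expected Outcomes foresees no adverse reactions other than those two.

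**Worsening.** The Discussion first notes that depression was the one symptom without an average change, and then says: "It is promising to see that cases of depression were not worsened during the trial". The closing paragraphs conclude: "Nearly all studied symptoms improved for all patients during the trial, and there was no worsening of symptoms recorded".

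**What the tables report.** Prior to the Trial and After The Trial give one mean per rated item, for 11 items and five patients. On the symptom scale, 1 is very severe and 10 is absent, so a falling score is a worsening.

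**The concern.** The sentence in During The Trial is the report's safety result, and it is absolute. A reader who stops there takes tolerability to be 0 of 5 affected. The later section describes patients as tired by the sessions, in need of time to recover from the treatment, and at risk of exhaustion that could distort the results. Both accounts cannot stand as worded.

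The conclusion that symptoms improved for all patients, with no worsening, reads as a statement about individuals. The figures tabulated beside it are averages, and an average can rise or stay level while some patients decline. That sentence sits beside the recommendation of PEMF as an alternative to prescription medication and the plan for a much larger study, so what it rests on should be clear.

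**Working it through.** **1. The two tolerability statements side by side.**

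- During The Trial: no patient reported a negative side effect, so 0 of 5.
- Reflections and Considerations: one patient is identified by number, so at least 1 of 5. The plural suggests at least 2. The true count could be anywhere from 1 to 5.
- What the tiredness is attributed to: the subject of the sentence is the twice-weekly schedule, but wider spacing "would allow patients to recover from PEMF treatment before their subsequent sessions". The wording therefore does not separate device effect from visit burden.
- How mild an effect may be and still be named a side effect: the risk section uses the term for headache or dizziness that was not severe and passed within 12 hours. No available text excludes tiredness.
- The mean fatigue rating improved from 5 to 6.8. That compares one answer before the trial with one after it and does not measure tiredness between sessions.

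**2. Reproducing the printed changes.** Inputs are the means in the two results tables, with n = 5. Sum = 5 × mean; net change = sum after − sum before; mean change = net / 5. All 22 means are multiples of 0.2, as equally weighted whole-number scores from five patients would give. The document says *weighted average* without giving weights, so equal weights and whole-number scores are assumptions here.

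| Item | Mean before → after | Sum before → after | Net | Mean change | Patients worse: possible range |
|---|---|---|---|---|---|
| Quality of life | 6 → 8 | 30 → 40 | +10 | 2.0 | 0–3 |
| Depression | 6.4 → 6.4 | 32 → 32 | 0 | 0 | 0–4 |
| Falling asleep | 5.6 → 8.2 | 28 → 41 | +13 | 2.6 | 0–3 |
| Flashbacks | 5 → 7.4 | 25 → 37 | +12 | 2.4 | 0–3 |
| Headaches | 4.6 → 6 | 23 → 30 | +7 | 1.4 | 0–3 |
| Fatigue | 5 → 6.8 | 25 → 34 | +9 | 1.8 | 0–3 |
| Anger | 4.8 → 7.4 | 24 → 37 | +13 | 2.6 | 0–3 |
| Daily tasks | 5.8 → 7.4 | 29 → 37 | +8 | 1.6 | 0–3 |
| Anxiety | 6.2 → 7 | 31 → 35 | +4 | 0.8 | 0–4 |
| Happiness | 6.2 → 8.2 | 31 → 41 | +10 | 2.0 | 0–3 |
| Satisfaction | 5.8 → 7.8 | 29 → 39 | +10 | 2.0 | 0–3 |

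All 11 printed changes are reproduced. Ten means rose, one was unchanged and none fell.

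**3. What the means allow for individuals.** The last column comes from enumerating every set of five paired whole-number scores from 1 to 10 with the printed sums. The upper limits can be checked by hand. If four patients worsen, the fifth can gain at most 9 and the four lose at least 4 together, so the net is at most +5. That fits depression (0) and anxiety (+4) but no other item (+7 to +13). Every range includes 0, and the upper ends need extreme scores. If no patient moved more than 1 point on depression, the range there is 0 to 2.

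**4. Depression exactly.** Let d₁ to d₅ be the five changes. The means give d₁ + … + d₅ = 32 − 32 = 0. If no patient worsened, every d is at least 0. Non-negative numbers that sum to 0 are all 0. So nobody worsened only if all five scores were unchanged. This does not need whole-number scores and holds for any fixed positive weights.

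**5. Improvement in every patient.** With whole-number scores, improvement in all five needs a net of at least +5. Depression (0) and anxiety (+4) fall short, so improvement for all patients is possible on at most 9 of the 11 items.

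**The case against.** The strongest reply concerns what cannot be seen here. The text that directly follows the side-effect sentence introduces the practitioner's verbal feedback from each patient and is not in the copy reviewed; it may already report the tiredness. The response charts are not shown either, and further patient-level accounts are missing. The statement that nothing in the report establishes the absence of worsening would therefore go too far. Only the narrower statement holds: the means do not establish it by themselves.

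It is also fair to say that tiredness may reflect the schedule, that the available text defines no adverse event, and that the risk section's remark on headaches is an observation rather than a threshold. The tiredness is openly disclosed and used to plan the next study, so a reader who infers concealment has no support in the document. What remains is that the absolute sentence and the later one disagree, and that the later one speaks of recovery from the treatment.

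On depression, the Discussion sets its remark just after noting no average change, so an average-level reading is natural. The closing conclusion can also be read symptom by symptom, and no mean fell. But that same sentence says the improvement was for all patients, which makes the individual reading a fair one too. It is ambiguous rather than plainly false.

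Finally, a reader might take the range of 0 to 4 as evidence that some patients got worse. It is not. It is a feasibility bound that includes 0, and the sponsor held the individual answers.

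**Conclusion.** The point holds as a minor wording correction to the safety statement and the conclusion.

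- The side-effect sentence implies 0 of 5; the later section implies at least 1 of 5. The exact number and the cause are unknown from the available text, and missing text may qualify the sentence.
- The group means do not by themselves support the closing conclusion when it is read at the level of individuals. For depression it is true of individuals under exactly one condition: five unchanged scores.
- Nothing here shows that any patient worsened, that the device caused the tiredness, or that a harm was hidden.

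The depression result needs only the two printed means and fixed positive weights. The ranges for the other items, and the limit of 9 of 11 items, also rest on whole-number scores; the ranges further assume equal weights and a 1 to 10 scale.

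**What to change.** **During The Trial.** Replace the absolute statement with one that reports tiredness with the twice-weekly sessions in N of 5 patients, with N taken from the practitioner's notes. If the notes give no count, write *number not recorded, at least Patient Three*. Add *no other negative effects were reported* only if the notes support it.

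**Closing conclusion.** Write *no mean rating fell (10 of 11 rose, depression unchanged)*, unless the before and after questionnaires can be linked by patient and show that no patient worsened on any item. If they can be linked, tabulate patients better, unchanged and worse for the 11 rated items.

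**Discussion.** Write *the mean depression rating did not change*, unless the linked pairs show all five scores unchanged.

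**A check without linkage.** Compare charts 1.10 and 2.2. With equal weights the depression totals are equal, so if the two charts show different sets of scores, at least one patient's rating worsened. Identical sets would not settle it, because patients could have exchanged scores.

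**Cost.** Three sentences reworded, one reading of existing notes, one look at two charts, and an 11-row table if the pairs can be linked. The tolerability statement becomes slightly less favourable; no efficacy mean changes.

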### After The Trial

Once the trial had been completed over the course of 3 weeks, patients were asked to complete the same questionnaire that was sent out prior to the clinical trial. In the table below, responses have been recorded as an average, with a percentage comparison of improvement or decline in symptoms.

Question	Average Score
Have you experienced or witnessed a life-changing event that caused intense fear, hopelessness or horror?	All patients recorded 'Yes'.
Rate Your Quality of Life	Average Score: 8 ( Improvement of >2 points )
Rate The Severity of Depression	Average Score: 6.4 ( No change )
Rate How Difficult It Is To Fall Asleep	Average Score: 8.2 ( Improvement of >2.6 points )
Rate The Severity of Flashbacks Relating to a Traumatic Event	Average Score: 7.4 ( Improvement of >2.4 points )
Rate The Severity of Headaches or 'Brain Fog'	Average Score: 6 ( Improvement of >1.4 points )
Rate The Severity of Fatigue	Average Score: 6.8 ( Improvement of >1.8 points )
Rate The Severity of Anger or Irritable Outbursts	Average Score: 7.4 ( Improvement of >2.6 points )

Rate How Difficult It Is To Complete Daily Tasks	Average Score: 7.4 ( Improvement of >1.6 points )
Rate The Severity of Your Anxiety	Average Score: 7 ( Improvement of >0.8 points )
Rate Your Level of Overall Happiness	Average Score: 8.2 ( Improvement of >2 points )
Rate Your Level of Satisfaction and Fulfilment In Life	Average Score: 7.8 ( Improvement of >2 points )

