## Illustrations

### Survey Prior To Clinical Trial

#### 1.1

Have you experienced either repeating dreams, flashbacks, or intense physical/emotional stress that relate back to the traumatic event(s)?

[figure not shown]
5 responses

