## 1.4

Do you have problems sleeping?

[figure not shown]
5 responses

1.5

Do you become increasingly irritable, angry, or engage in self-destructive behaviour?

[figure not shown]
5 responses

1.6

How long have your symptoms persisted?

[figure not shown]
5 responses

1.7

Do you have anger or irritable outbursts?

[figure not shown]
5 responses

1.8

Do you experience heightened version of anxiety, sensitivity, or depression?

[figure not shown]
5 responses

1.9

RATE YOUR QUALITY OF LIFE

[figure not shown]
5 responses

1.10

RATE THE SEVERITY OF DEPRESSION

[figure not shown]
5 responses

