### 1.16

#### RATE HOW DIFFICULT IT IS TO COMPLETE DAY-TO-DAY TASKS

[figure not shown]
5 responses

1.17

RATE THE SEVERITY OF YOUR ANXIETY

[figure not shown]
5 responses

1.18

RATE THE EFFICACY OF MEDICATION YOU HAVE RECEIVED FOR YOUR CONDITION, IF ANY

3 responses

[figure not shown]

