## Survey After Clinical Trial

### 2.1

#### RATE YOUR QUALITY OF LIFE

[figure not shown]
5 responses

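### The report says the same questionnaire was repeated, but only 12 of the 19 baseline items have an after-trial result, and the conclusions should be limited to those

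*Combined protocol and SAP*

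**What the plan says.** After The Trial states that once the three weeks were over "patients were asked to complete the same questionnaire that was sent out prior to the clinical trial". The Study Design section treats the before-and-after questionnaire as the basis of all findings. Duration of the Study, Study Design and the Clinical Trial Outline each require a questionnaire before and after treatment, but none lists its items.

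The baseline table under Prior to the Trial contains the life-changing-event question, six symptom-frequency questions, one question on duration ("How long have your symptoms persisted") and 11 ratings from 1 to 10. The after-trial table contains the life-changing-event question and the 11 ratings.

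The Illustrations chart the survey before the trial as items 1.1 to 1.20. Item 1.7 is "Do you have anger or irritable outbursts", with five responses, and item 1.18 is "RATE THE EFFICACY OF MEDICATION YOU HAVE RECEIVED FOR YOUR CONDITION, IF ANY", with three. The part headed "Survey After Clinical Trial" runs from 2.1 to 2.11.

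The conclusions at the end of Reflections and Considerations say that almost every symptom examined improved in every patient and that no deterioration was recorded.

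**The concern.** With five patients and no control group, the before-and-after comparison is the only evidence the study offers. A reader told that one questionnaire was given twice will assume that every baseline question has a follow-up answer, and that the closing statements about all symptoms rest on the full set. The tables and charts do not bear this out. The unreported items include avoidance and detachment, which nothing else in the after-trial table measures. At stake is the scope of the conclusions, not the size of any reported rating change.

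**Working it through.** **1. The plan's own figures.** Change = after-trial mean minus baseline mean.

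| Rating | Before | After | Difference | Stated |
|---|---|---|---|---|
| Quality of life | 6 | 8 | 2.0 | 2 |
| Depression | 6.4 | 6.4 | 0 | no change |
| Falling asleep | 5.6 | 8.2 | 2.6 | 2.6 |
| Flashbacks | 5 | 7.4 | 2.4 | 2.4 |
| Headaches or brain fog | 4.6 | 6 | 1.4 | 1.4 |
| Fatigue | 5 | 6.8 | 1.8 | 1.8 |
| Anger | 4.8 | 7.4 | 2.6 | 2.6 |
| Daily tasks | 5.8 | 7.4 | 1.6 | 1.6 |
| Anxiety | 6.2 | 7 | 0.8 | 0.8 |
| Happiness | 6.2 | 8.2 | 2.0 | 2 |
| Satisfaction | 5.8 | 7.8 | 2.0 | 2 |

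All 11 reproduce in size; ten rise and one is unchanged.

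**2. Rows in the results tables.**
- Before: 1 life-changing event + 6 frequency + 1 duration + 11 ratings = 19.
- After: 1 life-changing event + 11 ratings = 12.
- Without an after-trial row: 19 − 12 = 7, namely the six frequency items and duration.

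**3. Printed charts.**
- Before: 8 frequency or duration questions (1.1–1.8) + 9 ratings (1.9–1.17) + medication efficacy (1.18) + 2 ratings (1.19–1.20) = 20.
- After: 11 ratings (2.1–2.11).
- Without an after-trial chart: 20 − 11 = 9, namely 1.1–1.8 and 1.18.
- The after charts match the before charts in wording and relative order: 2.1–2.9 are 1.9–1.17, 2.10 is 1.19 and 2.11 is 1.20.

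**4. Reconciling tables and charts.** The life-changing-event question is tabulated both times and charted neither time. Items 1.7 and 1.18 are charted at baseline but tabulated neither time: 20 − 2 + 1 = 19. So at least 20 + 1 = 21 questions were put before the trial, and at least 11 + 1 = 12 after it. The charts are not the complete form, and a missing chart does not prove that a question was not asked.

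**5. What has no follow-up.**

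| Frequency item | Baseline answers (5 patients) | Related rating reported afterwards |
|---|---|---|
| Re-experiencing | daily 1, monthly 2, rarely 2 | flashbacks |
| Avoidance | daily 1, weekly 2, monthly 1, rarely 1 | none |
| Detachment | daily 4, monthly 1 | none |
| Sleep problems | daily 1, weekly 2, rarely 2 | falling asleep |
| Irritability | daily 1, monthly 3, rarely 1 | anger |
| Heightened anxiety, sensitivity or depression | daily 3, weekly 1, monthly 1 | anxiety, depression |

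Detachment has the most daily reports of any frequency item. The pairing in the last column is by subject matter; the documents do not make it.

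**6. Share of the symptom picture.** Leaving out the event and duration questions, the baseline table has 19 − 2 = 17 symptom or wellbeing items. Follow-up is reported for 11 of 17 (65%) and not for 6 of 17 (35%). A better mean is reported for 10 of 17 (59%).

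**7. The two possibilities.** If an item was not asked again, the same-questionnaire sentence is wrong for that item. If it was asked again, its answer is missing from the table. The answer may differ between items. Neither case supplies data for a claim of improvement, or of no worsening, on the six items.

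**The case against.** **The declared endpoint was kept.** The Study Summary describes the primary endpoint as scale ratings of symptoms, and all 11 ratings were repeated with matching wording, in the same relative order, on one defined scale. The document promised to compare averages, and frequency categories are not averages. This stands: the rating results are untouched.

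**Some omissions are harmless.** Symptom duration is not an outcome that a three-week treatment can change. Past medication efficacy has little reason to be asked again when nobody was on treatment during the trial. Item 1.7 overlaps with the anger rating and the irritability question. This also stands, and it is why the weight falls on the six frequency items, and on avoidance and detachment above all.

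**No worsening was in fact recorded.** Read literally, this is true of the mean ratings shown. But the closing statement speaks of the symptoms studied, and for six of them nothing is reported that could have shown worsening.

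**Two stronger readings are tempting.** A reader might infer that the ratings are not like for like, because the baseline ratings followed eight other questions and the later ones did not. The documents do not support this. The charts are incomplete, so the order and content of the later form are unknown. Only 1.1 to 1.3 refer directly to the traumatic event, and depression, the second rating after those questions, did not change. Nothing gives a direction or size for a context effect.

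A reader might also infer that "There were no changes to the initial plan for the clinical trial" is false. That sentence sits beside attendance and side effects and refers to a plan that never lists the questionnaire's items, so a departure from it is not shown.

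**Conclusion.** The concern holds as a reporting inconsistency with a consequence for the conclusions. The claim of a repeated questionnaire conflicts with 19 against 12 tabulated items and 20 against 11 charts. Six of the 17 symptom or wellbeing items tabulated at baseline (35%) have no reported follow-up, and two of the six are not covered by any rating. The closing statements on improvement and absence of worsening are unsupported for those items, whichever explanation is true.

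No error in the 11 rating changes has been shown, nor any bias in them from a change of form. The conclusion assumes that the tables and charts contain all the questionnaire results. Some pages were not in the text available for review, so an explanation there cannot be excluded.

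**What to change.** 1. Establish from the completed forms which items each patient was asked before and after the trial.
2. If the frequency items were asked afterwards, add their results to the after-trial table, and report item 1.7 at both times.
3. If they were not, replace the same-questionnaire sentence with a list of the items that were repeated, and say that the others were not collected again. The list should not be drawn from the charts alone, because the after-trial table reports a twelfth answer, on the life-changing event, that is not among the 20 charted questions.
4. In either case, limit the closing conclusions to items with results at both times. Unless follow-up answers are recovered, say plainly that change in avoidance and detachment was not reported.
5. In the planned larger study, fix the item list in the protocol and use the identical form at both times.

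The cost is a check of a small set of forms and edits to a few sentences and the results tables. The real price is that the stated conclusions become narrower.
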